12.5 Primary Endpoint

Kidney function measurements of eGFR will be calculated primarily based on the creatinine - based "Bedside Schwartz" equation (2009) (for children below 18 years of age) and the creatinine - based CKD-EPI equation (2009). For subjects reporting age 18 to 23 years old at screening visit 1 of ePHex the mean of child and adult equations will be used. Subjects eGFR will be calculated using the same equation used at the ePHex study baseline throughout the study. Supportive summaries may use alternative eGFR equations.

Change from baseline in kidney function (eGFR) over time (including both the ePHex and the ePHex-OLE study) will be calculated as each visit value minus the value at baseline (ePHex). Description of eGFR and change from baseline in eGFR values after 24 months of open-label Oxabact treatment will be considered the primary analysis, although 12 months will also be presented. Graphical presentations of the eGFR data over time will therefore be done based on the observed data per individual patient as well as scatter and/or spaghetti plots.

In addition, to describe if Oxabact treatment has a similar effect during the first 12 and 24 months in the 0 - 0 and P - 0 groups, change from second baseline in eGFR over time will be summarised as above.

Additional description of the data will be provided including summaries and graphs of observed eGFR mean values (mean, SD) and mean change from baseline and/or second baseline over time.

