If the models cannot be run because of the small sample size of the study, either or not in combination with too many missing data, then analysis will be limited to descriptive statistics and graphical displays as described.

All the analyses described above for eGFR are based primarily on the Creatinine-based “Bedside Schwartz” for children and CKD-EPI 2009 equations² for adults. For subjects aged between 18 and 23 years (both inclusive) of age, the mean of the children and adult equation results will be calculated as described in the appendix referred in section 11.1).

In addition, supportive analyses based on the Cystatin-C based CKiD for children and CKD-EPI 2012 equations³ for adults (see section 11.1) will be carried out, and similar analyses and presentations as for the Creatinine-based “Bedside Schwartz”/ CKD-EPI 2009 equation will be done. For Cystatin-C based equations, no modification for subjects between 18 and 23 years will be performed.

For children, height values are collected at each visit, and therefore the additional supportive eGFR values will need to be adjusted on a per-visit basis accordingly.

Adults only have one height collected at baseline, and this will be used throughout. Age will need to be determined at each visit, if not collected. Given that for most subjects no full birth date will be available, an estimation of age will be used following section 7.2.

² Children: $eGFR=41,3 \times (\text{height} / S_{Cr})$, Adults: $eGFR=141 \times \min(S_{Cr}/\kappa,1)^\alpha \times \max(S_{Cr}/\kappa,1)^{-1,209} \times 0,993^{\text{age}} \times \gamma$, with S_{Cr} = serum creatinine (mg/dL), $\kappa = 0,7$ (females) or $0,9$ (males), $\alpha = -0,329$ (females) or $-0,411$ (males), $\gamma = 1,018$ (female) or $1,159$ (black) or 1 (otherwise), age in years and height in m.

³ Children: $eGFR=39,8 \times (\text{height} / S_{Cr})^{0,456} \times (1,8/S_{cys})^{0,418} \times (30/BUN)^{0,079} \times 1,076^{\text{male}} \times (\text{height}/1,4)^{0,179}$, Adults: $eGFR=135 \times \min(S_{Cr}/\kappa,1)^\alpha \times \max(S_{Cr}/\kappa,1)^{-0,601} \times \min(S_{cys}/0,8,1)^{-0,375} \times \max(S_{cys}/0,8,1)^{-0,711} \times 0,993^{\text{age}} \times 0,969^{\text{female}} \times 1,08^{\text{black}}$, with S_{Cr} = serum creatinine (mg/dL), S_{cys} = serum cystatine-C (mg/L), $\kappa = 0,7$ (females) or $0,9$ (males), $\alpha = -0,248$ (females) or $-0,207$ (males), BUN = Blood Urea Nitrogen (mg/dL), age in years and height in m.

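### The SAP's primary adult eGFR equation does not define its sex/race factor for a subject who is both female and black

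*SAP*

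**What the plan says.** SAP section 7.6.1 states that the eGFR analyses are "based primarily on the Creatinine-based “Bedside Schwartz” for children and CKD-EPI 2009 equations" for adults. Footnote 2 gives the adult formula. Its κ and α are split by sex only, so each subject has exactly one value of each. Its last factor, γ, combines sex and race in one list: "1,018$ (female) or $1,159$ (black) or 1 (otherwise". The SAP prints decimal commas; decimal points are used below.

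The section then adds a second set of equations: "In addition, supportive analyses based on the Cystatin-C based CKiD for children and CKD-EPI 2012 equations" for adults. Footnote 3 gives that adult formula, and its sex and race terms are two separate powers, "0,969^{\text{female}} \times 1,08^{\text{black", so both apply to a black woman.

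Two rules limit who is exposed to γ:
- For ages 18 to 23, SAP 7.6.1 says that "the mean of the children and adult equation results will be calculated as described in the appendix referred in section 11.1".
- Protocol section 12.5 says: "Subjects eGFR will be calculated using the same equation used at the ePHex study baseline throughout the study".

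The protocol names "the creatinine - based CKD-EPI equation (2009") without coefficients, so footnote 2 is the only place in the supplied documents where γ is defined. SAP section 11.1 refers to Addendum 1 for programming conventions and for integration with ePHex data. That addendum was not supplied.

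**The concern.** Being female and being black are not mutually exclusive, but footnote 2 lists their factors as alternatives. White women, black men and all other men each get one value. A black woman gets two candidates with no order of precedence and no combined value. A programmer who codes the footnote literally must pick one, and the other factor is lost.

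This equation produces the primary variable. The study is small (18 subjects included, SAP section 2.4), individual profiles are a main form of presentation, and every eGFR table is planned under both the 2009 and the 2012 formulae. For an affected subject, part of the difference between those two sets could come only from how the factors were written. A mis-scaled baseline could also put her on the wrong side of the 60 mL/min/1.73 m² subgroup cut in SAP section 7.6.4.

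The analysis pools ePHex and extension data, and SAP section 7.1 leaves the first baseline to the ePHex SAP. If the two studies coded γ differently, the discrepancy would enter the change from baseline directly.

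**Working it through.** The plan states no result to reproduce here; the check is on the formula itself.

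**Inputs.** γ = 1.018 (female) and γ = 1.159 (black), from footnote 2. The subgroup cut of 60 is from SAP 7.6.4. The change of -5 is illustrative and equals in size the planning difference in SAP 2.4.

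**Step 1: product form.** If the factors multiply, as the corresponding terms do in footnote 3, then γ = 1.018 × 1.159 = 1.1799.

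**Step 2: literal readings against the product.** γ is a constant multiplier, so the relative difference is the same at every creatinine and age.

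| γ used | Ratio to product | Product-form 60 reads | Product-form change of -5 reads |
|---|---|---|---|
| 1.018 only | 1.018/1.1799 = 0.863 (13.7% low) | 51.8 | -4.31 |
| 1.159 only | 1.159/1.1799 = 0.982 (1.8% low) | 58.9 | -4.91 |
| both | 1 | 60 | -5 |

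The two literal readings differ from each other by 1.159/1.018 - 1 = 13.9%. That figure does not depend on whether the product is right.

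**Step 3: an example.** Assume creatinine 1.2 mg/dL and age 30. For a woman, footnote 2 gives 141 × (1.2/0.7)^-1.209 × 0.993^30 × γ = 59.5 × γ. With γ = 1.018, 1.159 and 1.1799 the eGFR is 60.6, 69.0 and 70.2.

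**Step 4: the subgroup cut.** With 1.018 only, product-form values from 60 up to 60 × 1.159 = 69.5 fall below 60. With 1.159 only, the range is 60 up to 60 × 1.018 = 61.1.

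**Step 5: ages 18 to 23.** The adult result is averaged with the child result, which has no sex or race term. If the two results were equal (an assumption), the shortfall would halve to 13.7/2 = 6.9% or 1.8/2 = 0.9%.

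**Step 6: group level.** Take one affected subject among 8 in an arm (16 planned, 1:1). At a change of -5 the arm's mean change moves by (5 - 4.91)/8 = 0.01 or (5 - 4.31)/8 = 0.09. At an eGFR of 60 the arm's mean level moves by (60 - 58.9)/8 = 0.13 or (60 - 51.8)/8 = 1.03.

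**Step 7: mixed coding, conditional.** If the ePHex baseline used the product and the extension used a single value, a subject stable at 60 would show an apparent change of 58.9 - 60 = -1.1 or 51.8 - 60 = -8.2.

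**The case against.** The strongest reply is that the SAP names a standard equation and footnote 2 is only a loose shorthand for it. An experienced programmer would code the named equation, and Addendum 1 may already hold the correct form. That is possible. But footnote 2 is the stated rule for the primary variable, and an addendum not supplied cannot be assumed to correct it.

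A reader might infer that the printed equation is wrong and that eGFR will be miscalculated for any black woman in the study. The documents do not support that:
- Footnote 3 is a different equation with different coefficients. Its form supports multiplying the 2009 terms by analogy but does not prove it. What the documents show is an undefined case and an inconsistency in form.
- Not every black woman is affected. Under the protocol's fixed-equation rule, a girl on Schwartz at ePHex baseline stays on it and never meets γ, and at 18 to 23 the adult result is only half of the average.
- Numbers by race and sex are not given. Race is collected and is a planned subgroup, but that does not show that any such subject was enrolled.

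It is also fair to say that the consequence is limited. Within one consistent derivation γ rescales level and change together and cannot reverse the sign of a change. The evaluation is descriptive, without formal testing, and the subgroup tables are optional.

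**Conclusion.** The point stands as a minor specification defect. Footnote 2 gives no unique γ for a black woman on the adult equation. The literal readings are 13.9% apart, whichever form is right. The 1.8% and 13.7% shortfalls rest on the assumption that the two factors should multiply. Their full size applies only to a black woman over 23, and only if the program follows the footnote literally. With one consistent coding, the effect on a group mean change is at most about 0.1 mL/min/1.73 m² for one subject among 8 at a change of -5. The effect on that subject's own profile and subgroup assignment can be material. If none of the 18 subjects is concerned, nothing in the results changes.

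**What to change.** Rewrite the last part of footnote 2 with two separate multipliers, in the same form as footnote 3: 1.018 if female, times 1.159 if black. Before doing so, confirm that form against the source of the named 2009 equation. Then check that Addendum 1, the analysis program and the ePHex baseline derivation all use it.

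The cost is one line in the SAP and a short program check. No design, sample size or data collection changes, since sex and race are already recorded.

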7.6.2 Key secondary endpoints

The key secondary endpoints will be presented using the FAS population, and all individual data will be listed as well.

Total plasma oxalate

The key secondary endpoint change from baseline in total plasma oxalate concentration, will be analysed using a similar analysis (descriptive plus supportive MRMM including the slopes) as proposed for the primary endpoint (see section 7.6.1), and no additional sensitivity analyses will be performed. Similar descriptive statistics per visit (absolute and change from baseline) and plots will be created.

Additionally, a combined plot for total plasma oxalate concentration and eGFR over time will be created using a double-axis display – this plot will be created for each subject, and a summary plot presenting mean +/- SE values per treatment group and overall will be made.

Summary statistics will also be created for the observed minimum and maximum total plasma oxalate concentration values during ePHex-OLE, as well as its changes from baseline using both baselines. Also, plots will be created to present the shift from baseline to the minimum or maximum value, combined for all subjects per treatment group and overall.

In addition, a frequency tabulation will be created based on the number of subjects achieving ‘near-normalization’ of total plasma oxalate concentration (<10 µmol/L) at least twice during 12 months and during 24 months of open-label treatment. This table will also include the response assessments for < 10 µmol/L during 12 months and during 24 months of open-label treatment.

Furthermore, percent change from baseline in total plasma oxalate concentration after 12 and 24 months of treatment will be displayed descriptively per treatment and overall, using both baselines.

Kidney stone events

Kidney stone events are defined as subject- or investigator reported symptoms (as in the CRF AE or PH medical history pages), or number of stones assessed by Ultrasound (US). As a consequence, three summary tables on stone events will be presented, as follows:

- Stone events during treatment, based on AE
- Stone events during treatment, based on US

Here, during treatment is defined as first to last dose date of ePHex-OLE. Where applicable, stones left and right will be combined into one overall kidney stone number for summary tables and analysis.

Descriptive statistics of the occurrence of kidney stones and the number of subjects with a stone event after 12 and 24 months of open label treatment will be presented per treatment group and overall, separately as based on AE and based on US datasets.

Descriptive statistics on stone events using the AE dataset will include a summary of days missed at school/work due to a stone event and other relevant data related to stone events.

Incidence rate of kidney stones is the rate at which kidney stone events occur in the population, and defined as the number of kidney stone cases per subject-year(s). The calculation of the incidence rate is the number of kidney stone occurrences during the study time period divided by the group of subjects susceptible to a stone event (i.e. the FAS), expressed as person-time and

calculated as sum of the treatment duration time of all subjects in the FAS. This calculation is accomplished as follows:

- Denominator: $\sum t_i$, where t_i = treatment duration of subject i in years (total # days divided by 365.25), where treatment duration is determined based on first and last dose date.
- Numerator: the total number of kidney stone occurrences during treatment (first to last dose date)
- Incidence rate=numerator/denominator

Since this analysis is done both after 12 months and after 24 months of treatment, in case of 12 months the date of visit 6 is used instead of last dose date.

The use of this measure implies the assumption that the incidence rate is constant of different periods of time. The incidence rates will be presented per treatment group. As these incidence rates are determined per treatment group, comparisons can be done using descriptive statistics of incidence rate difference (IRD) and incidence rate ratios (IRR). IRD and IRR are defined as follows, assuming the following exposure table:

			Treatment exposure	
			O - O	P - O
Outcome	12 months	Occurrences	a	B
		Person-time	PT1	PT2
	24 months	Occurrences	a	b
		Person-time	PT1	PT2

Then $IRD=(a/PT1) - (b/PT2)$ and $IRR=(a/PT1)/(b/PT2)$ is calculated for 12 months and 24 months. These will be presented in combination with a 95% CI.

If sample size allows it, for comparison between treatments on the total number of kidney stone events, an appropriate model fitting the specific count data will be used, if feasible considering the small sample size. This can be either a Poisson model or a Negative Binomial model, depending on the overdispersion. First a Pearson Chi-squared dispersion statistic is determined. When the dispersion statistic is close to one (i.e. mean is approximately the same as the variance), the Poisson model will be used. If the dispersion statistics however is larger than one (variance >> mean), it is more appropriate to use the Negative Binomial instead. If necessary, depending upon the number of zeros in the underlying data, a zero-inflated model will be used. This analysis is considered the last analysis in the hierarchical approach.

All other US data will be presented in a descriptive summary.

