1 SYNOPSIS

Name of Sponsor/Company

OxThera Intellectual Property AB.

Name of Investigational Product

Oxabact OC5.

Name of Active Ingredient:

Oxalobacter formigenes, strain HC-1.

Title of Study:

An open-label single-arm treatment extension study to evaluate the long-term efficacy and safety of Oxabact for patients with primary hyperoxaluria who completed study OC5-DB-02.

Planned number of sites/Countries

The study is planned to be conducted in the following countries: Germany, United Kingdom, Belgium, Spain, USA and Tunisia. 8-10 sites will be participating.

Phase of development:

Ш

Objectives:

Primary:

• To evaluate the efficacy of Oxabact following two years continued treatment in subjects who have completed the Oxabact OC5-DB-02 (ePHex) study.

Secondary:

 To obtain additional safety data from two years continued treatment with Oxabact.

Methodology:

This single arm, open-label international multi-center study (OC5-OL-02, ePHex-OLE) will evaluate the efficacy and safety of Oxabact treatment for an additional two years in subjects with Primary Hyperoxaluria (PH) who have previously been treated with Oxabact or placebo in the ePHex study. Subjects who consent to participate will, upon completion of the ePHex study, be seamlessly transferred from the ePHex protocol to this study. Baseline in this protocol is defined as the baseline of the ePHex study, unless otherwise stated.

At the start of the ePHex study, subjects had maintained renal function but with an estimated Glomerular Filtration Rate (eGFR) below the lower limit of the normal range (<90 ml/min/1.73 m²) and a total plasma oxalate concentration \geq 10 µmol/L. Subjects will not be re-tested for inclusion into the present ePHex-OLE protocol but values will be measured for their second baseline at the last visit (week 52) in the ePHex study (this applies to all parameters except for echocardiography and ultrasound of the kidneys which are assessed at week 48). If there is no seamless transition (delay >1

month) from the ePHex study to the ePHex-OLE study, a new clinic visit 0 will take place with applicable measurements for the second baseline.

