6 INVESTIGATIONAL PLAN

6.1 Background and Rationale

This study is an open-label, single arm, multi-centre study to evaluate the efficacy and safety of the long-term use (two years of open-label Oxabact treatment) of OC5 (*O. formigenes*) to stabilise/improve kidney function, stabilise/reduce plasma oxalate concentration, and to reduce oxalate deposits in PH patients. Included subjects will be the subjects who underwent treatment (administered either Oxabact or placebo) in the ePHex study and consented to participate in the ePHex-OLE study. At the start of the ePHex study, subjects had maintained renal function but with an eGFR below the lower limit of the normal ranges (<90 ml/min/1.73 m²) and a total plasma oxalate concentration ≥ 10 µmol/L at baseline. These criteria will not be re-tested for inclusion into the ePHex-OLE study protocol.

It is hypothesised that daily administration of *O. formigenes* facilitates the secretion of endogenously produced oxalate via the GI tract. Enteric elimination of oxalate may help to reduce oxalate deposits and eventually decrease the plasma oxalate level, thereby improving eGFR and kidney function as well as progression of myocardial function.

A natural history study in PH patients included in the Rare Kidney Stone Consortium (RKSC) Registry (Zhao et al., 2016) studied the key determinants for renal outcome in this patient population. The subjects included in the analysis had a mean eGFR of 73 ml/min/1.73 m². During a median follow-up of 3.9 years (1.0, 12.8), 20% of subjects developed ESRD. The most important progression factors for kidney deterioration in subjects with PH from this registry study are detailed in Table 4.

Table 4 Factors Univariately Associated with Incident ESRD among PH Patients without ESRD at Diagnosis

Variable	Hazard Ratio (95% CI)	p-value
PH1	13.17 (3.19-54.38)	<0.001
Age at Diagnosis	1.02 (1.00 to 1.04)	0.02
Uox, mmol/1.73 m ² per 24h	1.13 (0.94 to 1.37)	0.20
Uox, mmol/1.73 m ² per 24h (Q4)*	3.40 (1.40 to 7.90)	0.01
eGFR, ml/min per 1.73 m ²	0.96 (0.94 to 0.99)	0.002

^{*}Q4: Quartile 4 related to an urinary oxalate excretion of >1.87 mmol/1.73 m² per 24hr

Scientific evidence in support of eGFR change

The recently published KHI consensus paper on "Endpoints for clinical trials in Primary Hyperoxaluria" highlights the importance of preserving renal function and summarises the available literature on the rate of kidney function decline in patients with PH (Milliner *et al*, 2020):

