7 SELECTION AND WITHDRAWAL OF PATIENTS

7.1 Subject Inclusion Criteria

- 1. Signed informed consent (as applicable for the age of the subject).
- 2. Participation in and completion of the ePHex study.
- 3. Subjects who had received vitamin B6 during the ePHex study should maintain a stable dose. Subjects not receiving vitamin B6 during the ePHex study must be willing to refrain from initiating pyridoxine during study participation.

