14.2.16	Summary statistics for minimum and maximum total plasma oxalate values, including change from baseline. (FAS). Two baselines.
14.2.17	Total plasma oxalate concentration (unit) percent change from baseline over time (FAS). Two baselines.

14.2.18	Frequency tabulation on subjects with 'near-normal' total plasma oxalate levels (FAS). Two baselines.
14.2.19	Mixed Repeated Measures Model result total plasma oxalate. (FAS)
14.2.20	LS estimates total plasma oxalate. (FAS)
14.2.21	Slope results total plasma oxalate. (FAS).
14.2.22	Mean (+/-SE) total plasma oxalate versus time plot, per treatment (FAS). Similar plot for change from baseline.
14.2.23	Individual total plasma oxalate versus time plot (FAS). Similar plot for change from baseline.
14.2.24	Shift plots from baseline to minimum/maximum value for total plasma oxalate. (FAS).
14.2.25	Spaghetti plots per treatment group of the actual total plasma oxalate concentration values (FAS).
14.2.26	LS mean +/- SE plot total plasma oxalate (FAS)
14.2.27	Mean (+/- SE) plots eGFR/total plasma oxalate versus time using double axes (FAS) - Two calculation methods (2009 and 2012 formulae).
14.2.28	Mean (+/- SE) plots eGFR/total plasma oxalate versus time using double axes (FAS) - Two calculation methods (2009 and 2012 formulae).
14.2.29	Descriptive statistics kidney stone events (FAS), based on AE and US, respectively
14.2.30	Incidence rate of kidney stone events (FAS), based on AE and US, respectively
14.2.31	Descriptive statistics stone frequency by subgroup (FAS)
14.2.32	Descriptive statistics US data (FAS)
14.2.33	Statistical analysis stone frequency, based on AE and US, respectively
14.2.34	Descriptive statistics STE parameters (FAS) – raw and cfb
14.2.35	Descriptive statistics traditional echocardiography parameters (FAS) – raw and cfb
14.2.36	Descriptive statistics main STE/TE parameters (LVEF/GLS) by subgroup (FAS) – raw and cfb
14.2.37	Mean (+/-SE) main STE/TE parameters (LVEF/GLS) versus time plot, per treatment (FAS)
14.2.38	Individual main STE/TE parameters (LVEF/GLS) versus time plot, per treatment (FAS)

14.2.39	Descriptive statistics free plasma oxalate (FAS) – raw and cfb
14.2.40	Descriptive statistics free plasma oxalate by subgroup (FAS) – raw and cfb
14.2.41	Mean (+/-SE) free plasma oxalate versus time plot, per treatment (FAS). Similar plot for change from baseline.
14.2.42	Individual free plasma oxalate versus time plot (FAS). Similar plot for change from baseline.

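### The near-normalisation table for plasma oxalate ignores the month-0 value, so subjects already below 10 µmol/L, or stable near it, can be counted as achieving it on open-label treatment

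*SAP*

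**What the plan says.** - **The rule.** SAP 7.6.2 tabulates subjects with total plasma oxalate below 10 µmol/L "at least twice during 12 months and during 24 months of open-label treatment". It sets no condition on the starting value and does not require the two values to be consecutive.
- **A second row.** SAP 7.6.2 adds: "This table will also include the response assessments for < 10 µmol/L during 12 months and during 24 months of open-label treatment". Whether this means any single value or the value at the time point is not stated.
- **Population.** Key secondary endpoints use the FAS (SAP 7.6.2), and percentages are taken over the whole applicable analysis population (SAP 7.1).
- **Table shell.** SAP 12.3, Table 14.2.18: "Frequency tabulation on subjects with 'near-normal' total plasma oxalate levels (FAS). Two baselines". Under SAP 7.1 the second baseline applies only to subjects who had placebo in ePHex.
- **Entry level.** ePHex required "total plasma oxalate concentration ≥ 10 µmol/L at baseline" (Protocol 6.1). On the extension, the same section says: "These criteria will not be re-tested for inclusion into the ePHex-OLE study protocol". The eligibility lists in Protocol 7.1 and 7.2 contain no oxalate limit. The link to ePHex is "Participation in and completion of the ePHex study".
- **Status.** SAP 8 records the tabulation as an addition to the protocol. SAP 7.1 rules out formal testing.

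**The concern.** The table describes subjects as achieving a level during open-label treatment, but the rule looks only at open-label values. Two kinds of subject can meet it without any change after month 0: those already below 10 when open-label dosing starts, and those whose stable level is close enough to 10 that ordinary variation gives two low values.

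The attribution is weakest in the P-O group. A P-O subject who fell below 10 during the placebo year did so before any Oxabact, yet two further low values would enter that subject as achieving near-normalisation on Oxabact.

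In a small, open-label, untested study, a reader takes such a count largely at face value. A proportion that is higher at 24 months than at 12 could be read as a growing response when it partly reflects more opportunities to qualify.

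**Working it through.** The plan states no figure for this measure, so there is nothing to reproduce. The check has a textual part and a sizing part.

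**1. Text.** The near-normal range (below 10) is the exact complement of the ePHex entry criterion (10 or more). The rule, the FAS definition and the eligibility lists contain no month-0 condition. The two-baselines note does not supply one: an absolute threshold count does not depend on a change from baseline, no supplied text says how a baseline would enter it, and Oxabact-then-Oxabact (O-O) subjects have no second baseline under SAP 7.1.

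**2. Number of opportunities.** Protocol 6.2 schedules plasma oxalate at months 2, 4, 6, 8, 10 and 12 (6 values), then 15, 18, 21 and 24 (10 in all). With a fixed denominator and a cumulative rule, the 24-month count is at least the 12-month count.

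**3. Chance of meeting the rule with no change.** If each value independently falls below 10 with probability p, then P(at least 2 of n) = 1 − (1−p)^n − n·p·(1−p)^(n−1).

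| p | n = 6 | n = 10 |
|---|---|---|
| 0.10 | 0.11 | 0.26 |
| 0.20 | 0.35 | 0.62 |
| 0.30 | 0.58 | 0.85 |
| 0.50 | 0.89 | 0.99 |

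**4. By true level.** Assume log-normal visit-to-visit variation around a stable level L, with s = √ln(1+CV²) and p = Φ(ln(10/L)/s). Example with L = 11 and CV 20%: s = √ln(1.04) = 0.198 and p = Φ(−0.481) = 0.315. For n = 10, 1 − 0.685^10 − 10 × 0.315 × 0.685^9 = 1 − 0.023 − 0.105 = 0.87. The CVs are assumptions. Entries are by 12 / by 24 months.

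| L (µmol/L) | CV 10% | CV 20% | CV 30% |
|---|---|---|---|
| 9 | 1.00 / 1.00 | 0.99 / 1.00 | 0.98 / 1.00 |
| 11 | 0.27 / 0.53 | 0.61 / 0.87 | 0.72 / 0.94 |
| 12 | 0.02 / 0.04 | 0.29 / 0.56 | 0.51 / 0.79 |
| 15 | 0.00 / 0.00 | 0.01 / 0.02 | 0.08 / 0.20 |

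**5. A no-effect cohort.** In a simulation, subjects enter with one value of 10 or more, keep a stable level, have one month-0 value and attend all 10 visits. The median level before selection (12, 15 or 20 µmol/L), the between-subject log SD (0.35) and the CV (10–30%) are all assumptions. Ranges run over CV 10–30%, and the last four columns are at 24 months.

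| Median | Below 10 at month 0 | Counted, as written | Counted, of those below 10 at month 0 | Counted, of those 10 or more at month 0 | As previous column, two consecutive values |
|---|---|---|---|---|---|
| 12 | 8–21% | 16–46% | 81–82% | 11–37% | 6–21% |
| 15 | 4–12% | 8–28% | 72–78% | 5–22% | 3–12% |
| 20 | 1–5% | 2–11% | 57–72% | 2–9% | 1–4% |

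**6. In subjects.** SAP 2.4 reports 18 included. One subject is 1/18 = 5.6 percentage points. The extremes as written, 2.2% and 46.2%, correspond to 18 × 0.022 = 0.4 and 18 × 0.462 = 8.3 subjects.

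**The case against.** The strongest case against is that this is a minor descriptive display. The key secondary endpoint is change from baseline in total plasma oxalate. Near-normalisation is an added, untested frequency table, shown beside change, percent change, minimum and maximum shifts, individual plots and listings. The Protocol Synopsis, after saying "Subjects will not be re-tested for inclusion into the present ePHex-OLE protocol", goes on to say that second-baseline values are measured, so month-0 status is known and a careful reader of 18 profiles could find it. All of this stands and limits the weight of the point. It does not correct a summary count that labels such subjects as achieving the level.

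Against the ePHex baseline, where entrants were required to be at 10 or more, a value below 10 is a fall. For O-O subjects a low month-0 value may be a response to a year of Oxabact. That also stands. It is a reason not to remove these subjects, and not to restrict the denominator by a post-randomisation value.

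Addendum 1 and the table templates were not supplied and might define a split behind the two-baselines note. The SAP itself does not.

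A reader might infer more than the documents support:
- *Everyone below 10 at month 0 is counted.* Month 0 itself does not count, and two further low values are needed. In the simulation 57–82% of such subjects qualify by 24 months.
- *Entrants selected at 10 or more will regress below it.* They regress toward their own level, which may be well above 10.
- *A large spurious response is shown.* The high figures need true levels near 10. Drop-out (25% per year anticipated, Protocol 12.2) or levels rising as kidney function declines (Protocol 4.5.1) would lower them.

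**Conclusion.** The gap in the definition is certain from the text: the count ignores month-0 status, uses the former entry threshold, and cannot fall between 12 and 24 months. It can therefore attribute to open-label treatment a level that was present before it.

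The size is not known. About 2–46% of a no-effect cohort would be counted by 24 months, given stable levels, independent variation, complete visits, and the assumed medians and CVs. The documents supply no oxalate distribution, no within-subject CV and no number of subjects below 10 at month 0.

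It would be wrong to read this as inflating a type I error or invalidating the key secondary endpoint, since nothing is tested and the endpoint itself is change from baseline. The consequence is a misleading attribution in one descriptive table, which is worth correcting because the correction is cheap.

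**What to change.** In SAP 7.6.2 and Table 14.2.18, keep the full FAS and the existing rule, and make these changes:

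1. Within O-O and P-O, tabulate the count by month-0 status, defined for both groups as 10 or more versus below 10 at the last value before open-label dosing. Label the first stratum 'achieved'. Label the second 'already below 10 at open-label start: maintained / not maintained'.
2. Where ePHex data are integrated (SAP 7.1, option 1), show the same count for the double-blind year by randomised group, with the number of values available per subject. The ePHex oxalate schedule is not in these documents, so opportunities may differ. This reference matters because the split alone leaves 2–37% of those starting at 10 or more counted by 24 months in the no-effect simulation.
3. Optionally, add a supportive row requiring two consecutive values below 10. It lowers that figure to 1–21% but need not replace the stated rule.

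The cost is SAP wording and one revised table. Plasma oxalate is already scheduled at month 0 (Protocol Table 5). For seamless transfers that value is the ePHex week-52 result, so without integration it would have to be brought across or shown as unavailable. The downsides are small cells and a probably lower 'achieved' figure.
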